1.2 Objectives and Rationale

Our long-term goal is to help achieve epidemic control and the global targets of 90-90-90 through improved care delivery based on rigorous implementation research. The overall objective of this project is to demonstrate the effectiveness and longer-term sustainability of an innovative differentiated care delivery model for improving HIV treatment outcomes. The central hypothesis is that the integration of HIV care delivery into community-based primary care within group-based microfinance will improve retention and rates of viral suppression (VS) among people living with HIV (PLWH) in rural low-income settings in western Kenya via two related mechanisms: improved household economic status and easier access to care. The hypothesis is based on our strong feasibility and acceptability evidence of community-based care with group microfinance for NCDs,³⁰ the longstanding acceptability (since 2010) of our microfinance activities (currently >1300 groups and >43,000 people),³¹ and community-based HIV care delivery in our program.³² The rationale is that we need to implement and rigorously test specific differentiated care approaches in order to achieve sustained and sustainable approaches to achieve the 90-90-90 goals.

Figure 1. Schema of the cluster randomized trial

2. Overview of key activities during the cluster randomized trial

	Pre- basel ine	Basel ine	Visit 1	Visit 2	Visit 3	Visit 4	Visit 5	Visit 6	Visit 7	Visit 8	Visit 9	Visit 10
		Mon th 0	Mon th 1	Mon th 2	Mon th 3	Mon th 4	Mon th 5	Mon th 6	Mon th 9	Mon th 12	Mon th 15	Mon th 18
 Enrollment: Eligibility Screening Informed Consent Ascertain viral load data from patient medical records Alignment of patient/participant clinical appointments with ICB care schedule 	X	X										
Randomization of GISHE groups to integrated community-based care intervention or standard facility care	X											
Matching of standard care (SOC) patients to enrolled microfinance group participants on age, gender, county	X	X	X	X	X							
Administration of ICB care intervention (to MF+ICB groups only)		X	X	X	X	X	X	X	X	X	X	X
Collection of microfinance group performance/participation data (in MF+ICB and MF+SOC only)		X			X			X	X	X	X	X
Review AMRS medical record to coordinate care needs and delivery		X	X	X	X	X	X	X	X	X	X	X
Facility visits to collect retention in care information for Arm B participants of non-AMRS sites					X			X		X		X

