To evaluate the extent to which delivering integrated community-based care for HIV, diabetes and hypertension within microfinance groups affects hemoglobin A1C (HbA1c) level among people living with HIV (PLWH).	The secondary endpoint will be absolute mean change in hemoglobin A1C (HbA1c) level (mmol/mol) over the 18-month study period.	Mean change in HbA1c has shown to be associated with longer-term cardiovascular benefit, even when traditional control thresholds are not met.

 $^{^2}$ See the Addendum to the overall project protocol starting on page 100 for changes made to the primary endpoint.

OBJECTIVES	ENDPOINTS	JUSTIFICATION
Our working hypothesis is that A>B>C in terms of HbA1c level, where (A) represents		
microfinance groups receiving integrated community-based care, (B) represents		
microfinance groups receiving facility-based care, and (C) represents facility-based		
care without microfinance.		

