- The study assessments will be conducted at community locations that are convenient for participants
- We will hire appropriately-trained staff members to conduct recruitment and retention activities; many staff members have already been working with the MF groups for a number of years

Participant retention in the SOC arm: Research personnel will attempt to contact identified eligible SOC participant up to 2 times to invite them to enroll in Aim 1. Research personnel will attempt to contact each enrolled SOC participant up to two times to complete the 18-month follow up assessment (i.e., viral load and surveys). In the event that a participant cannot be located, their most recent viral load measurement will be ascertained from the patient's AMRS data to estimate viral suppression at 18 months.

5. Aim 1 RCT Methods: Randomization ⁴

Group randomization will occur after all consenting participants complete baseline assessments using a computer-generated sequence to randomize MF groups to receive either integrated community-based care (ICB) or standard of care. The randomization process will be conducted centrally by biostatisticians at Brown University.

6. Aim 1 RCT Methods: Intervention Delivery ⁵

Integrated care visits will occur monthly during months 1-6 of the trial, and then quarterly for the remaining months (7-18). Initial intervention group visits (months 1-6) will focus on acute non-HIV related needs and screening for NCDs, such as diabetes and hypertension. Facilities will be informed that participants will be receiving HIV care outside of clinic for the duration of the study, unless additional care is required (i.e., referral to facilities for worsening HIV, acute care, hospitalization, etc.). Protocols

⁴ See the Addendum to the overall project protocol starting on page 100 for changes made to the randomization process.

⁵ See the Addendum to the overall project protocol starting on page 100 for changes made to the schedule and format of intervention delivery.

for handling new opportunistic infections, suspected viral resistance, malignancy screening and diagnosis will follow established AMPATH care protocols.

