- HbA1C test: A hemoglobin A1C test will be conducted among all microfinance group members in the integrated care arm during the baseline visit and during the final 18-month visit in the community if their RBS > 7.8 mmol/L or if their FBS > 6.1 mmol/L. The baseline and endline tests will be sponsored by the study.
- Systolic and diastolic blood pressure will be assessed during each clinical evaluation conducted in the community using a routine blood pressure cuff.
- (2) one-on-one referrals of the patient by the clinical officer to a health facility for emergency or acute care needs that cannot be addressed in the community (i.e., becomes virally unsuppressed/viremic, presents with new opportunistic infection, is lost to follow up, has moved out of study county, or another reason).
- (3) group-level health education during which the clinical officer will discuss positive HIV management habits, and health lifestyle habits for managing chronic conditions, and GISHE group members will be able to ask questions together.

For one-on-one activities, each participant will be invited to a private location near their group meeting location (e.g., private room in a community hall, empty classroom in an empty school) to meet with the clinical officer. For group-level health education activities, groups will convene in their regular GISHE meeting location (e.g., in an empty community hall, outdoors away from other crowds).

Clinical encounter data, medication distribution data and data on referrals will be recorded in REDCap in the community and then transferred to the patient's medical record by the clinical officer when the clinical officer returns to the facility.

- 7. Aim 1 RCT Methods: Data collection, management, and analysis
- 7.1 Data Collection

The trial involves the collection and use of the following types of data. With the exception of viral load data which will be ascertained from and/or entered directly into patient medical records, data will be collected using mobile tablets with secure encryption and cloud-based data capture.

1. We will measure HIV viral load at study enrollment and at 18-months for all enrolled trial participants.

- 1.1 Baseline viral load will reflect the most recent viral load measurement available in the patient's medical record within the 12 months prior to their enrollment date.

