- 1.2 18-month viral load will be assessed using blood draws taken during the 18-month assessment in the community (for microfinance group members) and at the facility (for non-microfinance group members).
- 2. For clinical secondary outcomes, we will measure systolic blood pressure and hemoglobin A1c at baseline and 18-months for all 900 microfinance group members enrolled in the trial. Blood pressure will be measured in the community by the clinical officer using a blood pressure arm cuff. HbA1c will be measured in the community by the clinical officers using a point of care test.
- 3. For non-clinical secondary outcomes, we will measure retention in care on an ongoing basis for all enrolled trial participants. Retention in care will be based on study records (REDCap) for intervention recipients and on medical records for facility care patients.
- 4. For exploratory outcomes and mediation analyses, we will collect survey data from all enrolled trial participants: at enrollment and 18-months for all trial participants, with an additional round of survey data collection at month 9 for all microfinance group members. Surveys will be administered by a research assistant to participants in a private location in-person. Surveys will assess demographics, health insurance enrollment and utilization, social support (Oslo Social Support Scale-3), quality of life (adapted version of the MOS-HIV scale), psychological distress (Patient Health Questionnaire-4), self-reported ART adherence (based on the adapted ACTG Adherence Questionnaire), self-reported adherence to NCD medications (based on the extent of DOSE-Nonadherence Questionnaire), barriers to accessing care, patient satisfaction with care, felt HIV stigma (9-item measure of felt stigma validated in Kenya). The survey instrument is included in Appendix III. For exploratory outcomes, we will collect data on microfinance group performance (e.g., saving and lending activities, loan default rates) for all microfinance group participants. Microfinance group performance data will be collected on a quarterly basis and recorded via REDCap. The microfinance data collection tool is included in Appendix IV.

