7.1.1 Baseline assessments

Trained research assistants will conduct baseline assessments at the first regularly scheduled MF meeting following study start date. During the baseline visit, **participants in GISHE groups** will:

- Complete informed consent procedures which include consenting to provide access to their AMRS data (Appendix I)
- Be screened for hypertension and diabetes following routine AMPATH protocols (Appendix VIII)
- Complete the survey assessments (Appendix III)

Participants who receive standard of care at AMPATH facilities and agree to enroll in the study (Study Arm C), will also complete a baseline assessment at a facility or mutually agreed upon convenient location. During the baseline visit, **SOC participants** will:

- Complete informed consent procedures which include consenting to provide access to their AMRS data (Appendix II)
- Complete the survey assessments (Appendix III)

AMRS IDs will be verified for all trial participants at enrollment. In addition, a separate contact form will be completed for participant follow-up and kept separately from other study documents.

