7.1.2 Follow up assessments

For study participants in MF groups (MF + ICB and MF+SOC), follow up assessments to evaluate primary and secondary outcomes will be conducted in the field at 9- and 18- months. During follow up assessments, MF group participants will:

- Provide a blood draw for HIV viral load testing (study month 18 only)
- Provide a systolic blood pressure reading (study month 18 only)
- Provide an HbA1c point of care test, if clinically indicated (study month 18 only)
- Complete the survey assessments (study month 9 and 18)

Trained research assistants will work with the clinical teams to collect survey assessment data on mobile tablets. Clinical teams will record blood pressure and HbA1c results in the patient's medical records and in the study REDCap records. At 18 months, clinical officers and research assistants will transport blood samples from the community to the Eldoret reference lab for analysis. For participants who do not attend MF group meetings during assessment time points (months 9 and 18), research assistants will use participant's contact information to schedule follow-up meetings to collect data if participants are willing to meet outside of the regularly scheduled MF meeting time. We will access and review AMRS for data on secondary outcomes (i.e., retention in care and chronic disease composite score).

For study participants receiving SOC (Study Arm C), follow up assessments to evaluate primary and secondary outcomes will be conducted at AMPATH facilities when the patient returns for their HIV clinic visit at 18-months. During follow up assessments, SOC patients will:

- Provide a blood draw for HIV viral load testing
- Complete the survey assessments

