11. What concerns do you think patients may have about integrating HIV care into microfinance groups?

Probes:

- What do you think they may like about this integrated care model?
- What do you think they may dislike about this integrated care model?

Additional comments

12. Is there anything else that is important for me to understand about community-based care delivery from your perspective? How about microfinance groups? How about the integration of HIV care into microfinance groups?

Closing: Thank participant for their time. Remind participant about the confidentiality of the interview. Ask if they have any questions about anything that was discussed.

EXAMPLE: Thank you for your time and for sharing your thoughts with us. We want to remind you that your comments will remain confidential. Do you have additional questions or comments?

Appendix VIII: NCD screening protocol at study baseline (implemented in all microfinance groups (Study Arms A and B)) **Hypertension (HTN)** Diabetes (DM) Screening Screen for HTN in community groups¹ Screen for DM in community groups (study baseline) FBS < 6.0 mmol/L and FBS \geq 6.1 mmol/L or SBP < 140mmHg SBP ≥ 140mmHg or RBS \leq 7.7 mmol/L RBS \geq 7.8 m/mol/L and DBP < 90mmHg DBP > 90mmHg Perform HbA1C NOW test Discharge Patient needs confirmatory screening in 1 month HbA1C < 6.5 mmol/mol HbA1C ≥ 6.5mmol/mol Counsel on primary prevention; Patient has confirmed DM. begin or continue treatment Discharge Screening (confirmatory 1-month confirmatory screening not required Confirmatory screening for HTN in community group after 1 month) SBP > 140mmHg or SBP < 140mmHg and DBP < 90mmHg DBP > 90mmHg Discharge Patient has confirmed HTN; begin or continue treatment

SBP: systolic blood pressure; DBP: diastolic blood pressure; FBS: fasting blood sugar; RBS: random blood sugar; HbA1C: hemoglobin A1C. Screening for hypertension and diabetes was conducted in the community for all microfinance group members randomized to standard, facilitybased (usual) care and to microfinance group members randomized to the integrated, community-based care intervention.

Addendum to the overall project protocol

This addendum summarizes changes that were made to the overall project protocol after the start of Aim 1 data collection on November 25, 2020.

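### The documents contradict themselves on who is tested for the HbA1c-change secondary endpoint: all microfinance members, or only those meeting a glucose or clinical condition

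*Combined protocol and SAP*

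**What the plan says.** Section 3.4 defines the endpoint: "The secondary endpoint will be absolute mean change in hemoglobin A1C (HbA1c) level (mmol/mol) over the 18-month study" period. Four places then say who is tested.

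- **Section 7.1, item 2** (outcome data, Arms A and B): "we will measure systolic blood pressure and hemoglobin A1c at baseline and 18-months for all 900 microfinance group members enrolled in the trial". There is no condition.
- **Section 7.1.2** (follow-up of Arms A and B, introduced as serving the primary and secondary outcomes): "Provide an HbA1c point of care test, if clinically indicated (study month 18 only"). The indication is not defined.
- **Section 6.2** (intervention delivery, worded for Arm A): tests at baseline and at the "final 18-month visit in the community if their RBS > 7.8 mmol/L or if their FBS > 6.1 mmol/L". It does not say which visit's glucose counts.
- **Section 7.1.1 and Appendix VIII** (baseline, Arms A and B): members are to "Be screened for hypertension and diabetes following routine AMPATH protocols (Appendix VIII"). In that flowchart, "Perform HbA1C NOW test" appears to sit on the raised-glucose branch.

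Addendum item 7 takes Arm C out of the blood pressure and HbA1c endpoints. It does not say whether every member of Arms A and B was tested. Addendum item 10 revises the viral-suppression analysis only, so HbA1c stays under section 7.2. That section treats HbA1c change as a continuous outcome, handles dropout by inverse probability weighting, and gives no HbA1c analysis set.

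**The concern.** A reader cannot tell which members contribute to this endpoint, or whether the A versus B contrast keeps the randomised comparison.

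The intervention includes diabetes care, so it may change month-18 glucose and the clinical impression formed at that visit. If either decided who was tested at month 18, the pairs available for analysis would depend on something that treatment may alter. The weighting in section 7.2 would not address this: a member who attends month 18 and is left untested by rule has not dropped out.

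**Working it through.** The documents give no figure for this endpoint to reproduce. The only power statement, in section 3.4.2, concerns viral suppression. The check is therefore a comparison of the text, followed by algebra.

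**Step 1: which statements conflict.** Sections 6.2 and 7.1.2 can be read together if the clinical indication is the glucose trigger, and Appendix VIII fits that reading at baseline. Universal testing in section 7.1 cannot be reconciled with them. The firm conflict is thus universal versus conditional testing, and it already exists between sections 7.1 and 7.1.2, which both concern outcome data. In the section 7.1.2 list, viral load and systolic pressure carry no condition; HbA1c does.

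**Step 2: what conditional testing does to the contrast.** Within one arm, among members tested at baseline, let:

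- r = share who attend month 18 but are untested by rule
- q = share who drop out
- T, R, L = mean HbA1c change in those tested twice, those untested by rule, and those lost

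Mean over all baseline-tested members = (1 − r − q)T + rR + qL.

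Tested-twice mean minus that mean = T − [(1 − r − q)T + rR + qL] = r(T − R) + q(T − L).

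With u = r + q, and d = T minus the mean change of all untested members, this equals u × d. The shift in the A − B contrast is uA × dA − uB × dB.

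**Step 3: apply it.**

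- Universal testing: r = 0 in both arms. Only the dropout term remains, and with no dropout the shift is 0.
- Indication fixed at baseline: the members due for retesting are known before month 18, and among them r = 0. The contrast covers a subset of members, but one chosen on a baseline value.
- Testing decided by month-18 glucose or judgement: r can exceed 0, and R can differ from T by an amount that depends on arm.
- Strict null, with one rule and the same dropout process in both arms: uA = uB and dA = dB in expectation, so the shift is 0.

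Dropout weights are aimed at the q term only.

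**Step 4: put in numbers.** Section 7.1 implies 900 members with tests planned at both visits. For the conditional rules the documents give no trigger prevalence, no retest rate and no mean changes. None of uA, uB, dA and dB is available, so the calculation stops here.

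**The case against.** The strongest reply is that section 6.2 is a care rule for the intervention arm and section 7.1 is the outcome rule, so nothing conflicts. That fails for section 7.1.2, which is an outcome-assessment list covering both arms and carries its own condition. Section 6.2 also describes its baseline and endline HbA1c tests as paid for by the study.

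A second reply is that the indication may have been fixed at baseline, for instance by confirmed diabetes in Appendix VIII. This stands as a possibility. It would remove the post-randomisation selection, though not the conflict with section 7.1.

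A third reply is that any bias is hypothetical. This stands too.

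Two stronger readings are tempting, and the documents support neither.

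- **That the arms used different testing rules.** A reader might infer this because section 6.2 names only Arm A, and because month-18 glucose is specified there alone. But section 6.2 names only Arm A for the month-18 viral load as well, and section 7.1 and addendum item 3 show that blood for this was planned and collected across all microfinance groups. Addendum item 9 lists baseline screening for non-communicable disease as common to Arms A and B.
- **That the HbA1c result is biased.** This would require showing that testing was decided at month 18 and that the untested differed. The documents show neither.

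**Conclusion.** The contradiction is on the page, and confidence in it is high. It should be fixed, because the conditional wording, if followed at month 18, can leave the endpoint to a set selected after randomisation, and section 7.2 has no provision for that.

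The conclusion goes no further. Selection arises only if month-18 glucose or judgement decided testing. Neither the size nor the direction of any bias can be derived. The point concerns one secondary endpoint in Arms A and B; viral suppression is untouched. It takes no view on which testing rule is clinically right.

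**What to change.** 1. Reconcile sections 6.2, 7.1, 7.1.2 and Appendix VIII, and state the HbA1c rule that was applied in each arm at each visit.
2. Define the HbA1c analysis set by the baseline test, identically in Arms A and B. Confirm that this test came before randomisation, as section 5 states: "Group randomization will occur after all consenting participants complete baseline assessments".
3. Report by arm the numbers tested at baseline, at month 18 and at both. Report separately those who attended month 18 but were untested by rule and those who dropped out. Without that split, r and q cannot be told apart.
4. Only if month-18 testing was conditional, describe the tested-twice contrast as a selected comparison, and add a sensitivity analysis over plausible month-18 values for untested members, varied separately by arm.

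The cost is a text correction, one table of counts and at most one further analysis. Addendum item 10 reports completed primary analyses, so collection is probably closed; none of these steps needs new data.

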7.1.1 Baseline assessments

Trained research assistants will conduct baseline assessments at the first regularly scheduled MF meeting following study start date. During the baseline visit, **participants in GISHE groups** will:

- Complete informed consent procedures which include consenting to provide access to their AMRS data (Appendix I)
- Be screened for hypertension and diabetes following routine AMPATH protocols (Appendix VIII)
- Complete the survey assessments (Appendix III)

Participants who receive standard of care at AMPATH facilities and agree to enroll in the study (Study Arm C), will also complete a baseline assessment at a facility or mutually agreed upon convenient location. During the baseline visit, **SOC participants** will:

- Complete informed consent procedures which include consenting to provide access to their AMRS data (Appendix II)
- Complete the survey assessments (Appendix III)

AMRS IDs will be verified for all trial participants at enrollment. In addition, a separate contact form will be completed for participant follow-up and kept separately from other study documents.

